4.2.2 Handling of adverse events with missing data

Any AEs with incomplete onset and outcome (end) dates will be handled according to the following rules for classification as treatment-emergent. Such imputations will only be performed for these classifications; in the listings all data will be shown as recorded on the eCRF.

- If only the month and year are specified and the month and year of first dose is not the same as the month and year of onset, then use the 1st of the month.
- If only the month and year are specified and the month and year of first dose is the same as the month and year of onset, then use the date of first dose.
- If only the year is specified, and the year of first dose is not the same as the year of onset, then use January 1 of the year of onset.
- If only the year is specified, and the year of first dose is the same as the year of onset, then use the date of first dose.
- If the AE onset date is completely unknown, then use the date of first dose.
- Imputations for missing end dates will not be performed for classification as treatment-emergent as this is not required.

Adverse events with missing severity or causality will be regarded as ‘severe’ and ‘related’ respectively for the tabulations. There will be no imputation of any other missing data. Any AE with additional missing data that prohibits classification for a given tabulation will be excluded from that tabulation.

In case of uncoded AEs, these AEs should be designated as “UNCODED” at all MedDRA levels, and such AEs will be included in summary tables and subject listings based on this classification.

4.3 Interim analyses and data monitoring

Not applicable.

4.4 Multicenter studies

The data from all centers will be pooled for the purposes of the analysis. There will be no formal statistical evaluation of the effect of center on the results obtained

4.5 Multiple comparisons/multiplicity

Not applicable.

4.6 Use of an efficacy subset of subjects

Not applicable.

4.7 Active-control studies intended to show equivalence

Not applicable.

4.8 Examination of subgroups

The following subgroups will be used for the analysis of primary outcome variable.

- Indication: RA, PsA, AS and CD.
- Dosing regimen: Q2W and Q4W.
- Impaired hand function: baseline Cochin score ≥ 13.5 .

5 STUDY POPULATION CHARACTERISTICS

5.1 Subject disposition

A Subject disposition will include (at a minimum) summaries regarding screened and enrolled subjects, disposition by investigator, and reasons for discontinuation.

Summary tables of all subjects screened will be presented including reason for screen failures and disposition of subjects screened.

The number and percentage of subjects who completed the study, and who discontinued the study by discontinuation reasons will be summarized for subjects in the SS.

Study eligibility criteria will be listed and a separate listing of subjects who did not meet the eligibility criteria will be presented.

Subject disposition will be listed for all subjects screened. Listings of subject analysis sets, study discontinuation, and visit dates will be presented by subject including the relative day for the SS.

5.2 Protocol deviations

Important protocol deviations will be identified and classified by the deviation types. Following different important protocol deviation types will be classified: inclusion criteria deviation, exclusion criteria deviation, withdrawal criteria deviation, prohibited concomitant medication use, AE/SAE Deviation, and procedural non-compliance. Summary tables of the number and percentage of subjects with an important protocol deviation will be provided for the SS.

A listing of all important protocol deviations identified at the data evaluation meeting will be presented by subject for all subjects in the SS, and will include deviation type and description.

6 DEMOGRAPHICS AND OTHER BASELINE CHARACTERISTICS

6.1 Demographics

Tables with descriptive statistics (number of subjects, mean, SD, minimum, median, and maximum) and listings will be given for the demographic variables age (at time of informed consent), gender, racial group, ethnicity, weight at Screening, height at Screening, body mass index (BMI). Age and BMI will be summarized as a continuous variable and as categorical

variables. Age will be combined based on the following categories: ≤ 18 , $19- < 65$, ≥ 65 years. BMI will be summarized based on the following categories: < 25 , $25- < 30$, ≥ 30 kg/m².

BMI in kg/m² is calculated based on the height (in m) and the weight (in kg) using the formula:

$$BMI = \frac{Weight}{Height^2}$$

Data collected in the CRF for female subject's childbearing potential and birth control will only be listed

6.2 Other Baseline characteristics

Hand function will be assessed at the screening visit by the Cochin Impaired Hand Function questionnaire. Cochin score will be calculated from the Cochin Impaired Hand Function questionnaire at Visit 1 Screening. There are 18 questions scored from 0 to 5. Total score will be calculated as the sum of all individual score. If there is any missing value in individual score, total score will not be calculated. Total score should range from 0 to 90. Results will be summarized as a continuous variable and as categorical variables. Cochin score will be based on the following categories: < 13.5 , ≥ 13.5 at Screening.

A listing will be provided for Cochin Impaired Hand Function questionnaire at Visit 1 Screening.

6.3 Medical history and concomitant diseases

Medical history and ongoing medical conditions will be summarized by MedDRA SOC and PT overall and by dosing group and indication. The denominator for the percentages will be the number of subjects in the SS.

6.4 Prior and concomitant medications

Prior medications include any medications that started prior to the start date of study medication. Past medications are a subset of prior medications, and include prior medications with a stop date before the date of first CZP administration via e-Device. Concomitant medications are medications taken at least one day in common with the study medication dosing period. For this study, that will include from the date of first self-administration of CZP via e-Device up to the SFU visit.

In the case of missing data, the classification of medications as prior and/or concomitant will be performed as described in [Section 4.2.2](#). Imputations of missing data will be performed before calculation of relative study days.

The number and percentage of subjects taking prior medications will be summarized overall and by dosing group and indication, and by anatomical therapeutic chemical (ATC) class, presenting Anatomical Main Group (ATC Level 1), and PT. The number and percentage of subjects taking concomitant medications will be summarized similarly. Tables for prior and concomitant medications will be presented for the SS.

Prior and concomitant medications will be listed by dosing group and indication within dosing group for the SS. Prior and concomitant procedures will be listed for reported term by dosing group and indication within dosing group.

7 MEASUREMENTS OF TREATMENT COMPLIANCE

Compliance will be summarized based on the SS. Compliance will be examined in terms of completed injections, and will be calculated as:

$$\text{Percent compliance} = \frac{\text{number of completed injections}}{\text{number of expected injections}} \times 100$$

Where the number of injections expected is relative to the dosing group and when the subject finishes treatment. For example, for a subject on Q4W regimen prematurely discontinued from the study after Visit 1 due to AE, it is expected that this subject should complete 2 injections.

A summary of percent treatment compliance categorized as $\leq 50\%$, $> 50\%$ and $\leq 75\%$, and $> 75\%$ will be provided overall and by dosing group and indication.

8 OUTCOME ANALYSES

Outcome analysis will be performed on the SS overall and by dosing group and indication. All outcome variables will be listed.

All statistical analysis will be descriptive in nature. There is no formal statistical hypothesis testing or inferential analyses are planned. No p-values will be presented.

8.1 Statistical analysis of the primary outcome variable

The primary outcome variable is the proportion (%) of subjects able to self-administer safe and effective injections using the e-Device at Visit 2. Safe and effective self-injection will be evaluated by the healthcare provider (HCP) and is defined as:

- Complete Dose Delivery: Subject self-injected the complete dose of CZP as confirmed by a visual inspection of the CZP-cassette(s) which shows the PFS container to be empty and
- No AEs related to use of the e-Device (ADEs) that would preclude continued use of the e-Device for self-injection

For subjects with CD on the Q4W dosing regimen who will self-inject twice ($2 \times 200\text{mg CZP}$) at each visit, each injection will be evaluated for safety and effectiveness using the above criteria. The primary endpoint of safe and effective self-injection for subjects on the Q4W dosing regimen will be met only if both self-injections are determined to be safe and effective.

The number and proportion of subjects with safe and effective self-injections will be tabulated overall and by dosing group and indication. A subgroup analysis will be performed for subjects with impaired hand function. The 90% CIs for the proportion based on the Exact Binomial method will be reported as well.

8.1.1 Derivations of primary outcome variable

The primary endpoint of safe and effective self-injection will be met if both criteria are confirmed by the HCP and are recorded on the Study Medication Administration CRF form: (1) subject self-inject the complete dose of CZP as confirmed by visual inspection of the CZP-cassette(s) which shows the PFS container to be empty; (2) there are no AEs related to use of the e-Device (ADEs) that would preclude continued use of the e-Device for self-injection.

No imputation of missing data will be performed.

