8.1.2 Analysis of the primary outcome variable

The number and proportion (%) of subjects who meet the primary endpoint of safe and effective self-injection at Visit 2 will be summarized overall and by dosing group and indication. Subjects who completed dose delivery, and subjects who has no AEs related to use of the e-Device will also be presented. The number of subjects who administered the self-injection at Visit 2 will be used as the denominator to calculate the proportion (%). The corresponding 90% CI based on Exact Binomial method will also be presented.

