8.2 Statistical analysis of the secondary outcome variables

The secondary outcome variables will be summarized using descriptive statistics. All summary statistics will be presented overall and by dosing group and indication. A subgroup analysis will be performed for subjects with impaired hand function.

8.2.1 Proportion (%) of subject able to self-administer safe and effective injections at Visit 1

Safe and effective self-injection will be evaluated by the HCP at Visit 1 and is defined as:

- Complete Dose Delivery: Subject self-injected the complete dose of CZP as confirmed by a visual inspection of the CZP-cassette(s) which shows the PFS container to be empty and
- No AEs related to use of the e-Device (ADEs) that would preclude continued use of the e-Device for self-injection

For subjects with CD on the Q4W dosing regimen who will self-inject twice (2x200mg CZP) at each visit, each injection will be evaluated for safety and effectiveness using the above criteria. The endpoint of safe and effective self-injection for subjects on the Q4W dosing regimen will be met only if both self-injections are determined to be safe and effective at Visit 1.

The derivation of this secondary endpoint will follow the same algorithm as the derivation of the primary endpoint. No imputation of missing data will be performed.

The number and proportion (%) of subjects who meet the endpoint of safe and effective self-injection at Visit 1, as well as subjects who completed dose delivery, and subjects who has no AEs related to use of the e-Device will be summarized overall and by dosing group and indication. The number of subjects who administered the self-injection at Visit 1 will be used as the denominator to calculate the proportion (%). The corresponding 90% CI based on Exact Binomial method will also be presented.

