10.2 Adverse events

10.2.1 Adverse event (IMP)

An adverse event (AE) is any untoward medical occurrence in a patient or clinical investigation subject administered a pharmaceutical product that does not necessarily have a causal relationship with this treatment. An AE can therefore be any unfavorable and unintended sign (including an abnormal laboratory finding), symptom, or disease temporally associated with the

use of a medicinal (investigational) product, whether or not related to the medicinal (investigational) product.

In this study, safety reporting requirements apply to all constituents of the IP (including CZP, the e-Device auto-injector, and the CZP-cassette) per 21 CFR 320. Adverse events related to use of the e-Device (ADEs) (including the CZP-cassette) will be summarized separately. Adverse events will be summarized by the frequency and percent of subjects having one or more of the events in question. Planned summaries include overall AEs, AEs by intensity, AEs by relationship to study drug, SAEs, AEs leading to withdrawal, AEs leading to death, ADEs, SADEs, and AEs of special interest.

Treatment-emergent AEs (TEAE) will be summarized overall and by dosing group and indication. Treatment-emergent AEs (TEAE) are those with onset date at or after the first self-injection with the e-Device up to 70 days after the last self-administration of study medication with the e-Device.

The incidence of TEAEs will be summarized by MedDRA SOC, high level term, and PT. Tables with incidences of classified TEAEs by maximum intensity, by relationship, and by subject number will be provided. Furthermore, the incidence of all TEAEs, serious TEAEs, TEAEs leading to study discontinuation and/or permanent withdrawal of study medication, TEAEs leading to death, and AE of special interest will be summarized. In addition, an overall summary table will be provided.

For each AE the following information will be listed for the SS: AE term (verbatim term), date of onset, pattern of event, whether or not the AE was classified as a SAE, as an AE of special interest, intensity, relationship to study medication, relationship to study device, action taken with study medication, other action taken, outcome, date of outcome, and whether the AE led to study drug discontinuation or to study discontinuation.

TEAEs with incidence of above reporting threshold of 5% of subjects will be summarized.

For all TEAEs the following variables will be calculated:

- Duration

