10.2.2 Adverse device effect (investigation device)

An adverse device effect (ADE) is an AE related to the use of an investigational device.

The incidence of ADEs and serious ADEs will be summarized separately by MedDRA SOC, high level term, and PT. Each ADE will be listed for the SS.

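### A subject withdrawn for a device-related AE between the visits can stay a Visit 1 success and leave the Visit 2 denominator, so neither composite success proportion need show the failure

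*SAP*

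**What the plan says.** The endpoint has two criteria: complete dose delivery, and absence of a device-related AE that would rule out further use of the e-Device. SAP 8.1.1 takes both from what is "confirmed by the HCP and are recorded on the Study Medication Administration CRF form". It does not name the AE page as a source, gives no period over which the second criterion is judged, and imputes nothing.

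For Visit 1, SAP 8.2.1 says "Safe and effective self-injection will be evaluated by the HCP at Visit 1" and "The derivation of this secondary endpoint will follow the same algorithm as the derivation of the primary endpoint". Its denominator is the subjects who injected at Visit 1. For Visit 2, SAP 8.1.2 says "The number of subjects who administered the self-injection at Visit 2 will be used as the denominator to calculate the proportion". Both sections also plan a row for subjects without a device-related AE, but do not state that row's source or window.

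Elsewhere, SAP 10.2.1 lists for each AE the onset date, "relationship to study device, action taken with study medication", and "whether the AE led to study drug discontinuation or to study discontinuation". SAP 10.2.2 tabulates ADEs and adds: "Each ADE will be listed for the SS". SAP 5.1 plans counts of subjects "who discontinued the study by discontinuation reasons will be summarized for subjects in the SS". Protocol 12.1 and 12.3.1 assign the primary variable to all subjects in the FAS, that is, everyone dosed with the e-Device. SAP 3.9 records no change to protocol-defined analyses.

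**The concern.** The study asks whether trained subjects can use the e-Device safely and effectively. Someone who stops because of a device-related AE is a failure on the very property that the second criterion measures. That subject's absence from Visit 2 is therefore not unrelated to the outcome: the denominator rule removes the subject for a reason that the endpoint is meant to capture.

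Estimation is the whole output of this study. Someone reading only the success table could see 100% at both visits and would have to combine it with the disposition and ADE outputs to find the failure. No planned table crosses device relationship with discontinuation or ties either to the endpoint.

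**Working it through.** **Tracing one subject through the rules.**

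1. The subject injects at Visit 1, is observed on site for 30 minutes (Protocol 7.2), and the HCP records both criteria as met. HCP evaluation is scheduled only at Visits 1 and 2 (Protocol Tables 5–1 and 5–2).
2. The visits are 2 or 4 weeks apart (SAP 2.3). In that interval a device-related AE starts. Protocol 7.2 foresees AEs arising outside site visits, and Protocol 6.3 provides for withdrawal after a severe or serious injection site reaction. The subject withdraws.
3. Visit 1: nothing instructs the HCP to revise the entry, so under SAP 8.2.1 it can stand as a success.
4. Visit 2: no injection takes place, so SAP 8.1.2 leaves the subject out. The early-discontinuation mapping in SAP 3.2.2 moves assessments to a scheduled visit but creates no injection.

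**Size.** The plan states no figure to reproduce: the study is not powered, and the documents give no rate for this event. Inputs from SAP 2.4 are at least 60 subjects using the device at Visit 1, at least 15 per dosing group, and at least 10 with impaired hand function. The interval is the SAP's own exact binomial 90% CI. Assumptions: k subjects withdraw in this way, and all other injections succeed.

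For x successes in n:
- lower limit = 5% quantile of Beta(x, n − x + 1)
- upper limit = 95% quantile of Beta(x + 1, n − x)
- when x = n, the lower limit is 0.05^(1/n) and the upper limit is 100%. For example, 0.05^(1/59) = 0.950.

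As planned, Visit 2 is (n − k)/(n − k). Counting the k subjects as failures gives (n − k)/n.

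| n at Visit 1 | k | Visit 2 as planned | Counted as failures |
|---|---|---|---|
| 60 | 0 | 60/60 = 100% (95.1–100) | no change |
| 60 | 1 | 59/59 = 100% (95.0–100) | 59/60 = 98.3% (92.3–99.9) |
| 60 | 2 | 58/58 = 100% (95.0–100) | 58/60 = 96.7% (89.9–99.4) |
| 60 | 3 | 57/57 = 100% (94.9–100) | 57/60 = 95.0% (87.6–98.6) |
| 15 | 1 | 14/14 = 100% (80.7–100) | 14/15 = 93.3% (72.1–99.7) |
| 10 | 1 | 9/9 = 100% (71.7–100) | 9/10 = 90.0% (60.6–99.5) |

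One event lowers the lower limit by 95.0 − 92.3 = 2.7 points overall, 80.7 − 72.1 = 8.6 points at n = 15, and 71.7 − 60.6 = 11.1 points at n = 10.

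**Chance that it arises at all.** With event probability r per subject, the chance of at least one among 60 is 1 − (1 − r)^60. At assumed r of 0.5%, 1%, 2% and 5%, this is 26%, 45%, 70% and 95%.

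**The case against.** - **The event is reported elsewhere.** True. The ADE tables, the tables of AEs leading to discontinuation and the disposition summary all use the Safety Set, which includes this subject. A reader might infer that the plan hides the event, or that no planned percentage can show it; the documents support neither. The row for subjects without a device-related AE might also show it at Visit 1, where the denominator includes the subject. The text does not settle whether that row uses AE data or merely repeats the form entry. What stands is that the composite success proportions need not show it.
- **The Visit 1 form may be corrected.** Possible. Protocol 11.3.1 allows eCRF corrections with a reason and refers to completion guidelines that are not available here; Protocol 11.3.2 requires consistency checks. The documents therefore establish silence, not a certain misclassification. General data cleaning is still not a derivation rule.
- **The planned analysis answers the stated objective.** The objective is ability to self-inject at Visit 2, and an assessment made at the visit is a legitimate reading. That is a reason to keep the primary analysis, and the fix does so. It does not explain why no companion figure covers all subjects in the FAS.
- **The scenario is narrow.** Also fair. The AE must be device-related, beyond the usual injection effects that Protocol 10 excludes from AEs, and lead to withdrawal within 2 to 4 weeks. An injection site reaction need not be device-related. The table shows what one subject is worth, not an expected bias.
- **Counting an injection that never took place as failed looks like imputation.** It would be if presented as an injection result. Defined as a composite in which stopping for a device-related AE is itself the failure, it is not.

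**Conclusion.** The point holds in a limited form. With no window for the device-AE criterion and a Visit 2 denominator of injectors only, a subject withdrawn for a device-related AE between the visits can fall outside the failures at both visits. This depends on the Visit 1 form not being revised afterwards.

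The effect on the overall estimate is small: 1/60 = 1.7 percentage points per subject. It is larger at the planned minima, at 1/15 = 6.7 points for a dosing group and 1/10 = 10 points for the impaired-hand subgroup. These sizes rest on assumed event counts and on all other injections succeeding; with no such event nothing changes.

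It would go too far to conclude that the primary endpoint is invalid or that a formal decision is at risk. The study has no hypothesis test and no success threshold. The change is worth making because the exclusion is tied to what the endpoint measures and the data needed are already planned.

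**What to change.** Keep the primary endpoint, its assessor and its denominator.

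1. In SAP 8.1.1, state that the device-AE criterion is an at-visit assessment. In SAP 8.1.2 and 8.2.1, state the source and window of the row for subjects without a device-related AE.
2. In SAP 8.1.2, add one supplementary Visit 2 proportion with its 90% exact CI, overall, by dosing group and in the impaired-hand subgroup. Add to the denominator, as failures, subjects who injected at Visit 1 but not at Visit 2 and had a device-related AE, with onset on or after the Visit 1 injection, that led to discontinuation of study drug or study. Label it a composite in which stopping for a device-related AE is a failure, not an imputed injection result.
3. Word the window as on or after the injection, because SAP 4.2.2 sets unknown onset dates, and some partial ones, to the date of first dose. Include those cases.
4. Count only AEs recorded as related to the study device. SAP 4.2.2 defaults missing causality to related without separating drug from device, so footnote AEs with missing device relationship instead of defaulting them.
5. Footnote the Visit 2 table with the number who did not inject because of an ADE.

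A separate Visit 1 supplementary table is unnecessary, since the Visit 2 figure counts the same subjects.

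The cost is a few SAP sentences, one supplementary table and a footnote, with no new eCRF field. The supplementary figure may be slightly lower than the primary. Leading to discontinuation is only a proxy for precluding further use: it misses a precluding ADE in a subject who stays in, or a withdrawal coded to another reason.
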